#### 4.2.20.4 Primary Analysis of Exploratory Endpoint #12

The primary analysis for this exploratory endpoint will be conducted as per section 4.2.18.4.

#### 4.2.20.5 Additional Analyses of the Exploratory Endpoint #12

The analysis will be repeated in the FAS using an alternative population level summary where the Cox proportional hazards model will include randomised treatment group and the following baseline variables: age (as a cubic spline), sex (female, male), participant recruitment country, presence of heart failure (yes/no), diabetes (yes/no), RAASI use (yes/no), CKD stage and baseline  $K^+$  (mild HK defined by  $5.0 < K^+ \leq 5.5$  and moderate/severe HK defined by  $5.5 < K^+ \leq 6.5$  mmol/L) as independent variables.

#### **4.2.20.6 Subgroup Analyses**

Not Applicable.

#### **4.2.21 Exploratory Endpoint #13 (All-cause hospitalisations, ED or outpatient visits)**

*Time to first occurrence of all-cause hospitalisations, ED visits or outpatient visits at any time post-discharge up to 180 days in each arm.*

##### **4.2.21.1 Definition**

- Population: Full analysis set
- Endpoint: Time to first occurrence of any component of the composite outcome at any time post-discharge up to 180 days inclusive.
- Intercurrent event strategy: Participants who discontinue of treatment will continue to be followed up to the first component of the composite endpoint (treatment policy strategy). Participants who require rescue therapy for HK or have RAASI down-titration (including discontinuation) will continue to be followed up to the first component of the composite endpoint (treatment policy strategy). Participants who require any hospital admission, ED visit, or outpatient visit will be considered an event (composite variable strategy). Participants who die of any cause will be censored at the date of death. Participants who are lost to follow-up will be censored at the date of loss to follow-up. Participants who do not have an event by 180 days post-discharge will be administratively censored at the date of 180 days post-discharge.
- Population level summary (analysis): Kaplan-Meier plots of the survival function for the SZC and SoC treatment groups will be presented. Log-rank test for testing will be used to calculate a two-sided p-value, Cox proportional hazards ratio for estimation, with randomised treatment group (reference level SoC) as the independent variable. The HR and the two-sided 95% confidence interval will be presented. The risk difference and two-sided 95% confidence interval will be presented (as per section 4.2.2.2) at 180 days post-discharge.

##### **4.2.21.2 Derivations**

Time to first occurrence will be defined as the earliest date of (all-cause hospitalisation, all-cause ED visits, outpatient visit, date of death, loss to follow-up, date of 180 days post-discharge) – date of randomization + 1.

##### **4.2.21.3 Handling of Dropouts and Missing Data**

Participants who are lost to follow-up will be censored at the date of discontinuation as recorded on the participant's disposition form.

#### **4.2.21.4 Primary Analysis of Exploratory Endpoint #13**

The primary analysis for this exploratory endpoint will be conducted as per section 4.2.18.4.

#### **4.2.21.5 Additional Analyses of the Exploratory Endpoint #13**

The analysis will be repeated in the FAS using an alternative population level summary where the Cox proportional hazards model will include randomised treatment group and the following baseline variables: age (as a cubic spline), sex (female, male), participant recruitment country, presence of heart failure (yes/no), diabetes (yes/no), RAASI use (yes/no), CKD stage and baseline  $K^+$  (mild HK defined by  $5.0 < K^+ \leq 5.5$  and moderate/severe HK defined by  $5.5 < K^+ \leq 6.5$  mmol/L) as independent variables.

#### **4.2.21.6 Subgroup Analyses**

Not Applicable.

### **4.2.22 Exploratory Endpoint #14 (eGFR slope)**

*Rate of change in (slope) eGFR between treatment arms.*

#### **4.2.22.1 Definition**

- Population: Full analysis set
- Endpoint: Change in eGFR between treatment arms
- Intercurrent event strategy: Participants who discontinue of treatment will have all available eGFR measurements included (treatment policy strategy). Participants who require rescue therapy for HK or have RAASI down-titration (including discontinuation) will have all available eGFR measurements included (treatment policy strategy). Participants who require any hospital admission or ED visit will have all available eGFR measurements included (treatment policy strategy). Participants who die of any cause or are lost to follow-up will have all measurements up to death or loss to follow-up included (hypothetical strategy).
- Population level summary (analysis): Change in eGFR will be analysed with a MMRM approach where the dependent variable is post randomisation eGFR and with fixed terms for randomised treatment group (reference level SoC), eGFR at randomisation, participant recruitment country, time from randomisation (days), and the interaction of treatment group (reference level SoC) by time from randomisation with random effects for participant, intercept and slope. The covariance structure will be unstructured. The coefficient estimates, standard error, 95% CI for coefficient estimates, and p-values will be reported.

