1.3 Schedule of Activities

Table 1 Schedule of Activities

Procedure	In-hospital phase (1 to 21 days) ^a			Outpatient phase (Visits 4 to 10)								E/D ^b	Follow-up phase	Details in CSP Section or Appendix
	Screening	Baseline ^a	Day of discharge from the hospital ^b	+7 days n	+30 days ^{c,h,} n	+60 days ^{c,h,} n	+90 days ^{c,h,} n	+120 days ^{c,h,n}	+150 days ^{c,h,n}	+180 days ^{c,h,n} (EOT)				
Visit	1	2	3	4	5 (phone)	6 (phone)	7	8 (phone)	9 (phone)	10			11	
Visit Window (+/-)				1	6	6	6	6	6	6			3	
Informed consent	X													
Inclusion and exclusion criteria	X													Sections 5.1 and 5.2
Randomisation			X											Section 6.2
Routine Clinical Procedures														
Demography	X													
Complete physical examination ^d	X													Section 8.2.1
Targeted physical examination ^e			X	X			X			X	X	X		Section 8.2.1
Medical history	X													
Concomitant medication	At every visit and may be conducted by phone if not tied to a visit													Section 6.7
Vital signs ^f	X	X	X	X			X			X	X	X		Section 8.2.2

Procedure	In-hospital phase (1 to 21 days) ^a			Outpatient phase (Visits 4 to 10)							E/D ^h	Follow-up phase	Details in CSP Section or Appendix
	Screening	Baseline ^a	Day of discharge from the hospital ^b	+7 days ⁿ	+30 days ^{c,h,n}	+60 days ^{c,h,n}	+90 days ^{c,h,n}	+120 days ^{c,h,n}	+150 days ^{c,h,n}	+180 days ^{c,h,n} (EOT)			
Visit	1	2	3	4	5 (phone)	6 (phone)	7	8 (phone)	9 (phone)	10		11	
Visit Window (+/-)				1	6	6	6	6	6	6		3	
Routine Safety Measurements													
Adverse events	At every visit and may be conducted by phone if not tied to a visit											Section 8.3	
Urine pregnancy test (women of child-bearing potential only)	X												
Clinical safety laboratory assessments (including urine dipstick) ^g		X	X				X			X	X		Section 8.2.4
Electrocardiogram	X		X	X			X			X	X	X	Section 8.2.3
Study Assessments													
Local laboratory K ⁺ ⁱ	X		X	X			X			X	X	X	Section 8.1.1
Central laboratory K ⁺ ^j		X	X				X			X	X		Section 8.1.1
Data collection on hospital admissions and ED visits (with HK and all-cause), ICU visits, outpatient visits, use of rescue therapy, RAASi dose changes/discontinuations, dialysis initiation, and eGFR (site visits)				X	X	X	X	X	X	X	X	X	Section 8.8

Procedure	In-hospital phase (1 to 21 days) ^a			Outpatient phase (Visits 4 to 10)								E/D ^h	Follow-up phase	Details in CSP Section or Appendix

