
 To evaluate the effect of continuing SZC as part of the discharge medications, compared to SoC, in the change in eGFR 	
 Rate of change in (slope) eGFR from inpatient phase to 90 and 180 days post-discharge respectively, in each arm.

 To evaluate the effect of continuing SZC as part of the discharge medications, compared to SoC, in the incidence of dialysis initiation 	
 Time to first occurrence of dialysis initiation in each arm at any time post-discharge up to 180 days.

 To evaluate the effect of continuing SZC as part of the discharge medications, compared to SoC, in reducing the incidence of ICU admissions 	
 Time to first occurrence of ICU admissions in each arm at any time post-discharge up to 180 days.

• To evaluate the effect of continuing SZC as part of the discharge medications, compared to SoC, on the ability to continue RAASi	
• Descriptive summary of use of, and changes in use of, RAASi, at up to 90 and 180 days post-discharge, respectively, in each arm.
--	--

Abbreviations: AE = adverse event; ECG = electrocardiogram; ED = emergency department; eGFR = estimated glomerular filtration rate; HK = hyperkalaemia; HR = hazard ratio; ICU = intensive care unit; K⁺ = potassium; LOS = length of stay; NK = normokalaemia or normokalaemic; RAASi = renin-angiotensin-aldosterone system inhibitor; SoC = standard of care; SZC = sodium zirconium cyclosilicate.

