#### **4.2.22.4 Primary Analysis of Exploratory Endpoint #14**

A MMRM will be fitted in the FAS with eGFR measurements as the dependent variable and randomised treatment group (reference level SoC), time from randomisation, country and the interaction of treatment group (reference level SoC) by time from randomisation with random effects for participant, intercept and slope. The covariance structure will be unstructured. The coefficient estimates, standard error, 95% CI for coefficient estimates, and p-values will be reported. The interaction term of treatment group by time from randomisation will provide the evidence of any difference in slope of eGFR by randomised treatment group. An interaction term $>0$  will demonstrate an increase in eGFR in the SZC arm compared to SoC.

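### SAP 4.2.22.1 and 4.2.22.4 give two different models for the eGFR slope (exploratory endpoint #14), and the treatment-by-time term in 4.2.22.1 does not estimate the slopes from the inpatient phase to Day 90 and to Day 180

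*SAP*

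**What the plan says.** Protocol Section 3 (Table 3) defines the endpoint as "Rate of change in (slope) eGFR from inpatient phase to 90 and 180 days post-discharge respectively, in each arm". The SAP overview (Section 4.2.1) repeats that definition.

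SAP 4.2.22.1 specifies a mixed model "where the dependent variable is post randomisation eGFR". Its fixed terms besides treatment are "eGFR at randomisation, participant recruitment country, time from randomisation (days), and the interaction of treatment group" by time. It adds "random effects for participant, intercept and slope" and an unstructured covariance. The overview row carries the same model.

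SAP 4.2.22.4, the primary analysis section, reads differently: "A MMRM will be fitted in the FAS with eGFR measurements as the dependent variable". It does not limit the outcome to post-randomisation values and has no eGFR-at-randomisation covariate. It names the treatment-by-time interaction as the evidence on slope and says that a value above zero "will demonstrate an increase in eGFR in the SZC arm compared to SoC". The model in Protocol 9.4.3.3 (item 14) also has treatment, days post-discharge and their interaction, with no post-randomisation limit.

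The schedule of activities (Protocol 1.3) has two relevant rows. The row "Clinical safety laboratory assessments (including urine dipstick"), whose central panel includes eGFR, is marked at baseline, discharge, Day 90, Day 180 and early discontinuation. The data-collection row, which ends with eGFR at site visits, is also marked at Day 7 and follow-up.

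**The concern.** The endpoint starts in hospital, but the 4.2.22.1 outcome starts after randomisation. When the discharge value is only a covariate, whatever happens between discharge and the first later sample is absorbed by the treatment main effect. The term that the SAP reads as the slope difference does not see it. A kidney effect that appears early and is then held could be reported as no difference in slope.

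The two SAP sections can also give different answers from the same data, and the text does not say which one governs. Finally, the endpoint names two slopes, one to each horizon, while a single linear interaction yields one number.

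**Working it through.** The documents give no figure for the eGFR slope, so there is none to reproduce. The check works out what each model's treatment-by-time term would estimate.

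**Inputs.** Visits come from Protocol 1.3. Following SAP 4.2.22.2, time is the date difference plus 1, so discharge, Day 90 and Day 180 take the values 1, 91 and 181. The 52 participants per arm are from Protocol 9.2.2. Assumed, because the documents do not give them: between-patient SD 15 mL/min/1.73 m², slope SD 4 per year, residual SD 5 (range 3 to 8). The expected terms below do not change over that residual range; only the standard errors do.

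**What the term measures.** Let D(t) be the arm difference in eGFR at day t, with D(0) = 0 by randomisation. With outcomes at Days 90 and 180 only, the interaction is [D(180) − D(90)]/90 per day. The endpoint is D(90)/90 and D(180)/180.

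**Illustration: 2 units gained by Day 90, then held.** The slope difference to Day 90 is 2/90 × 365.25 = 8.12 per year. To Day 180 it is 2/180 × 365.25 = 4.06 per year. The 4.2.22.1 term is (2 − 2)/90 = 0.

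| Model and eGFR visits | Expected interaction, per year |
|---|---|
| 4.2.22.1, Days 90 and 180 | 0.00 |
| 4.2.22.1, Days 7, 90 and 180 | 3.84 |
| 4.2.22.1, Days 7, 90, 180 and follow-up | 3.39 |
| 4.2.22.4, discharge, Days 90 and 180 as outcomes | 4.06 |

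No row returns 8.12. If the 2 units arise by Day 7 instead, the 4.2.22.1 term is 0.00 even with Day 7 values included.

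**Linear divergence of 2 per year from discharge.** Every version returns 2.00, so the 4.2.22.1 term is then unbiased. Its precision is poorer with Days 90 and 180 only: SE 5.68 per year (3.47 to 9.04 over the residual range), against 2.92 (1.86 to 4.57) with discharge as an outcome. The ratio is 5.68/2.92 = 1.95. For residual error alone, the two-point slope SE is √2·s/90 and the three-point SE is s/√(2 × 90²) = s/127.3, a ratio of 2.0. Adding Day 7 to the 4.2.22.1 model brings its SE to 3.03.

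**Covariance.** A random intercept, a random slope, their covariance and a residual are 4 parameters. Two common time points supply 3 distinct elements (two variances and one covariance), so the mapping has rank 3. With times 0, 90 and 180 the rank is 4. With two scheduled values, the model is therefore identified only through variation in visit dates or through extra samples. The effects listed as participant and intercept are also the same effect.

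**The case against.** A reader might infer that the slope cannot be derived at all. The documents do not support that. Section 4.2.22.4 can take the discharge value as an outcome. Under linear trajectories the 4.2.22.1 interaction is the slope difference. Even with Days 90 and 180 only, (main effect + interaction × time)/elapsed days returns 8.12 and 4.06 exactly, and the SAP reports all coefficients. What remains is that the SAP does not specify this combination, and that with Day 7 included it returns 5.52 and 4.68.

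A reader might also infer that no eGFR is planned after discharge except at Days 90 and 180. The site-visit eGFR row is marked at Day 7, early discontinuation and follow-up; Protocol 8.2.4 allows unscheduled samples; and SAP 4.2.22.1 uses all available values. Against this, Protocol 8.2.4 has clinical chemistry done centrally and only local potassium at Day 7, and the site-visit row refers to the resource-use section (8.8). The two rows conflict and must be reconciled. The zero interaction, the roughly doubled SE and the identification problem hold only if two common time points are all there is.

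A third tempting inference is that eGFR after dialysis must be excluded. Keeping values after rescue is a stated treatment-policy choice, the documents give no frequency of dialysis after discharge, and excluding those values would create informative missingness of its own. It is an estimand trade-off, not an error.

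**Conclusion.** The point holds as a mismatch between endpoint and model. The two SAP sections differ, the 4.2.22.1 interaction omits change before the first post-randomisation sample, and one linear term cannot supply both named slopes. In the illustrated case the reported term is 0.00 or 4.06 per year depending on which section is coded, against slope differences of 8.12 and 4.06.

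The zero rests on eGFR coming only from the scheduled chemistry at Days 90 and 180, on no contribution from early-discontinuation or unscheduled samples, and on an assumed plateau of 2 units. With Day 7 values the loss is smaller when the effect builds up to Day 90, but the Day 90 slope is still not recovered. The SEs rest on the assumed SDs. Discharge is taken as the inpatient anchor because 4.2.22.1 itself uses eGFR at randomisation; the central panel is also drawn at baseline, so the SAP should name the anchor.

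The endpoint is exploratory and outside the testing order in SAP Table 5. No confirmatory conclusion changes, but the model should be settled before it is programmed.

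**What to change.** Replace 4.2.22.1 and 4.2.22.4 (and the matching row in 4.2.1) with one model:

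- Outcome: eGFR at discharge (Visit 3, time zero), Day 90 and Day 180.
- Terms: visit as a category, treatment-by-visit with arm means constrained equal at discharge, and country; unstructured residual covariance, no random effects.
- Report: the arm difference in change from discharge to Day 90 and from discharge to Day 180, each divided by elapsed time, as the two slope differences.
- State which visits supply eGFR, and reconcile the two rows of the schedule.
- Reword the last sentence of 4.2.22.4: a value above zero means a slower decline or greater rise in eGFR on SZC than on SoC.

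The cost is SAP text and code; discharge chemistry is already scheduled. There are two small downsides. Values outside the analysis visit windows are not used. The protocol's interaction with days post-discharge becomes secondary, which should be recorded in SAP Section 2 as a change to the planned analysis.

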#### **4.2.22.2 Derivations**

Time from randomisation will be calculated a date of eGFR measurement – date of randomisation + 1.

#### **4.2.22.3 Handling of Dropouts and Missing Data**

Participants who die or are lost to follow-up are assumed to be missing at random and that eGFR measurements would behave similarly to other participants in the same treatment group with similar covariate values.

#### **4.2.22.4 Primary Analysis of Exploratory Endpoint #14**

A MMRM will be fitted in the FAS with eGFR measurements as the dependent variable and randomised treatment group (reference level SoC), time from randomisation, country and the interaction of treatment group (reference level SoC) by time from randomisation with random effects for participant, intercept and slope. The covariance structure will be unstructured. The coefficient estimates, standard error, 95% CI for coefficient estimates, and p-values will be reported. The interaction term of treatment group by time from randomisation will provide the evidence of any difference in slope of eGFR by randomised treatment group. An interaction term $>0$  will demonstrate an increase in eGFR in the SZC arm compared to SoC.

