Assuming a 20% drop-out rate from enrolment to randomisation and a 20% drop out post-discharge (post-randomisation), approximately 163 participants will be enrolled, resulting in approximately 130 participants discharged and randomised, to achieve 104 evaluable participants (52 per arm).

Note: “Enrolled” means a participant's, or their legally acceptable representative's, agreement to participate in a clinical study following completion of the informed consent process. Potential participants who are screened for the purpose of determining eligibility for the study, but are not assigned treatment in the study, are considered “screen failures”, unless otherwise specified by the protocol.

Intervention Groups and Duration:

All participants will be treated with SZC as per local label (correction and/or maintenance treatment) during the in-hospital phase. The duration of in-hospital phase will be 1 to 21 days post-enrolment; medical monitor's approval may be sought for allowing longer duration hospital stays for specific participants.

At discharge, participants who are NK (K^+ between 3.5 and 5.0 mmol/L, inclusive) and have been started on a maintenance dose for SZC will be randomised in a 1:1 ratio to one of the following arms and subsequently enter the outpatient phase:

- Arm A: Participants discharged with SZC, as per local label, to manage HK until end of outpatient phase
- Arm B: Participants discharged with SoC, as per local practice, to manage HK until end of the study.

Note: Participants intended to receive a K-binder at discharge (as per the site routine medical practice) will not be randomised and will be discontinued from the study. Still, it is allowed that participants randomised into Arm B have any K-binder prescribed at Day 7 post-discharge (or after Day 7 post-discharge), to treat confirmed HK or in case there is an increase in K^+ level since discharge that, in the investigator's opinion, requires therapy.

The duration of outpatient phase will be approximately 180 days.

After the outpatient phase, participants will enter into the follow-up phase which will last 7 days. Study drug will be discontinued for participants in Arm A. These participants will be treated as per local practice (SoC). Participants in Arm B will continue SoC treatment.

The total study duration for each participant will then be approximately 6 months.

Adjudication Committee: Yes

Statistical Methods:

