Kaplan-Meier plots of the survival function for the SZC and SoC treatment groups will be presented. A log-rank test will be used to calculate a two-sided p-value. A Cox proportional hazards ratio will be used for analysis with randomised treatment group, and other covariates described in the SAP. The HR and the two-sided 95% confidence interval will be presented.

11. Duration of time on K-binders from initiation in the first instance of K-binder use post-discharge up to 180 days in each arm.

Kaplan-Meier plots of the survival function for the SZC and SoC treatment groups will be presented. A log-rank test will be used to calculate a two-sided p-value. This exploratory endpoint will be analysed using a Cox proportional hazards ratio with randomised treatment group, and other covariates described in the SAP. The HR and the two-sided 95% confidence interval will be presented.

12. Time to first occurrence of rescue therapy use to treat HK at any time post-discharge up to 180 days in each arm.

This exploratory endpoint will be analysed per exploratory endpoint #10.

13. Time to first occurrence of all-cause hospitalisations, ED visits or outpatient visits at any

time post-discharge up to 180 days in each arm.

This exploratory endpoint will be analysed per exploratory endpoint #10.

14. Rate of change in (slope) eGFR between treatment arms.

An MMRM analysis with randomised treatment group as a main effect, days post-discharge, an interaction effect between randomised treatment group and days post-discharge, as well as other covariates described in the SAP will be used to estimate the slope of eGFR by randomised treatment group.

15. Time to first occurrence of dialysis initiation at any time post-discharge up to 180 days in each arm.

This exploratory endpoint will be analysed per exploratory endpoint #10.

16. Time to first occurrence of ICU admissions at any time post-discharge up to 180 days in each arm.

This exploratory endpoint will be analysed per exploratory endpoint #10.

17. Use of RAASi at 90 and 180 days post-discharge by treatment arm.

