### 3.3.4 Multiplicity/Multiple Comparisons

To control for type I error, a hierarchical testing procedure will be followed when formally testing the primary and secondary efficacy analysis endpoints. The hierarchical testing procedure will follow a stepwise algorithm where each endpoint is only formally tested if the preceding null hypothesis is rejected (two-sided p-value < 0.05). If the preceding null hypothesis is not rejected, then the evaluation of the endpoint will be reduced to that of an exploratory endpoint. The testing order for the primary and secondary efficacy analysis endpoints is displayed in Table 5:

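### The SAP's reading of the eGFR slope result ties a demonstration to the sign of the interaction estimate and calls a difference in slopes an increase (minor, wording)

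*SAP*

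**What the plan says.** Exploratory endpoint #14 concerns the rate of change in eGFR. Protocol Section 3 (Table 3) defines it as "Rate of change in (slope) eGFR from inpatient phase to 90 and 180 days post-discharge respectively, in each arm". Protocol 9.4.3.3 says that the mixed model "will be used to estimate the slope of eGFR by randomised treatment group". Neither place says what sign or size of result would support which conclusion.

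SAP 4.2.22.4 fits a repeated-measures mixed model with treatment (SoC as reference), time from randomisation, country and the treatment-by-time interaction. On reporting, SAP 4.2.22.1 states: "The coefficient estimates, standard error, 95% CI for coefficient estimates, and p-values will be reported". The same commitment appears in 4.2.22.4. That section then says of the interaction term that it "will provide the evidence of any difference in slope of eGFR by randomised treatment group", and closes by stating that an interaction above 0 "will demonstrate an increase in eGFR in the SZC arm compared to SoC". The closing sentence mentions no interval, p-value or threshold.

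SAP 3.3.4 applies the hierarchical procedure "when formally testing the primary and secondary efficacy analysis endpoints". Table 5 lists the primary and six secondary endpoints. The eGFR slope is not among them.

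**The concern.** The closing sentence is the only one in SAP 4.2.22 that links a result to a conclusion, and it has two weaknesses.

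1. **Sign is not demonstration.** A point estimate above 0 is compatible with no difference, or with a difference in the other direction. Elsewhere the SAP states its threshold (significance at 0.05 in 4.2.2.1, two-sided p below 0.05 in 3.3.4). Here it states none. The comparable potassium model in 4.2.13.4 carries no such sentence.
2. **A slope difference is not an increase.** The interaction compares two rates of change. It does not say whether eGFR on SZC went up or down.

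The participants have chronic kidney disease or reduced eGFR, so a statement about kidney function would be noticed. A prespecified sentence using the verb *demonstrate* could be cited in support of an imprecise estimate, or of an apparent rise where there was only a slower fall.

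**Working it through.** The documents give no effect size, standard deviation, power or error rate for the eGFR slope, so there is no planned figure to reproduce. The check needs only the model form.

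**Inputs.** Model and reference level: SAP 4.2.22.4. Reported quantities: SAP 4.2.22.1 and 4.2.22.4. For the simulation only, 65 per arm, from approximately 130 randomised (Protocol 1.1) in a 1:1 ratio ("will be randomised in a 1:1 ratio to one of the following arms"): 130 / 2 = 65.

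**Step 1: the sign under no difference.** Let b3 be the interaction coefficient. If b3 = 0, its estimate divided by its standard error is approximately standard normal.

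- P(estimate > 0) = 1 − Φ(0) = 0.500
- P(lower limit of the two-sided 95% CI > 0) = 1 − Φ(1.96) = 0.025

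Neither value depends on the sample size or on the variability of eGFR. A simulation of 10,000 trials gave 0.494 and 0.024. It assumed 65 per arm, measurements at days 0, 90 and 180, a true slope of −4 mL/min/1.73 m² per year in both arms, a slope SD of 6 per year and a residual SD of 4.

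**Step 2: the sign when SZC is truly worse.** Expressing the true interaction in units of its own standard error avoids assuming an SD.

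| True b3 / SE | P(estimate > 0) | P(lower 95% limit > 0) |
|---|---|---|
| 0 | 0.500 | 0.025 |
| −0.5 | 1 − Φ(0.5) = 0.309 | 0.0069 |
| −1 | 1 − Φ(1) = 0.159 | 0.0015 |

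**Step 3: what a positive interaction means.** Write the time-related part of the model as b2 × time + b3 × SZC × time, with SoC as reference.

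- Slope on SoC = b2
- Slope on SZC = b2 + b3
- b3 > 0 is equivalent to: slope on SZC > slope on SoC
- eGFR rises on SZC only if b2 + b3 > 0, that is b3 > −b2

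So b3 > 0 is not enough for a rise whenever b2 is negative. For illustration, take assumed true slopes of −6 on SoC and −2 on SZC (mL/min/1.73 m² per year). Then b3 = −2 − (−6) = +4. The interaction is positive while eGFR falls in both arms.

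**Step 4: what is already available.** The SoC slope b2 is one of the coefficients to be reported. The SZC slope b2 + b3 is a linear combination from the same fit. SAP 4.2.22.4 does not explicitly plan to present the two slopes, although the protocol specifies the endpoint by arm.

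**The case against.** The best reply is that the closing sentence is a key to the sign of the coefficient. With SoC as reference, a positive value favours SZC, and nothing more is meant. The paragraph has already promised the standard error, confidence interval and p-value, and has just described the term as evidence of a difference in slope. On that reading any reasonable analyst would use the interval. The 50% is then simply a property of any symmetric estimator. The closing words of the sentence also make the increase relative to SoC, so it need not mean that eGFR rises. Finally, this is one of 17 exploratory endpoints, and no success decision depends on it.

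Much of this stands. A reader might infer that the SAP sets up a sign-only decision rule, so that with no true effect the trial would report a renal benefit about as often as not. The documents do not support that, because the interval and p-value for the same coefficient are committed to in the same paragraph. Nor do they support saying that a slower decline will certainly be misreported as a rise. That is a risk of the wording.

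What the reply does not remove is the verb. Reporting an interval does not say how it will be used, and the one sentence that states a conclusion does not refer to it. The relative phrasing softens the word increase, but still does not tell a reader that the quantity is a difference in rates of change.

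**Conclusion.** The point holds as a minor wording defect. Followed literally, the sentence treats a positive sign as a demonstration. That sign occurs with probability 0.50 under no difference, against 0.025 if the two-sided 95% interval must lie above 0. These two figures rest only on an approximately normal, unbiased estimate. The slope argument is algebra and needs no assumption; the −2 and −6 slopes are purely illustrative.

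The effect is confined to how one exploratory result is interpreted. The model, the reported quantities, the testing hierarchy and the type I error of the formally tested endpoints are unaffected. No further numerical size is offered. Error rates for particular eGFR differences would need SDs that the documents do not give and a settled set of measurement times. The schedule of activities (Protocol 1.3) lists eGFR collection at site visits, which include Day 7, so a calculation from Days 90 and 180 alone may not match the planned data.

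**What to change.** Replace the last sentence of SAP 4.2.22.4 with:

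> An interaction estimate above 0 indicates a more positive (or less negative) eGFR slope on SZC than on SoC. It will be interpreted with its two-sided 95% CI, and a CI that includes 0 will not be taken as evidence of a difference. The estimated slope in each arm with its 95% CI will be presented, as the protocol specifies slopes by arm.

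The cost is a few lines of SAP text and one extra output from the model already planned. The interval for the interaction is already to be reported, and the arm-specific slopes need no new data. The only thing given up is the option of describing a positive but imprecise estimate as a demonstration.
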